### 8.3.5. Pharmacokinetic/Electrocardiography Analyses

The Cardiac SAP will provide details on the planned PK/electrocardiography analyses.

The concentration-QTc analysis, based on  $\Delta\Delta\text{QTcF}$ , will be reported separately. That is, for the placebo adjustment, the individual  $\Delta\text{QTcF}$  for placebo calculated at a specific timepoint is subtracted from  $\Delta\text{QTcF}$  for the same subject on OM at the same timepoint to generate  $\Delta\Delta\text{QTcF}$ . The relationship between OM plasma concentration and  $\Delta\Delta\text{QTcF}$  will be investigated by linear mixed-effects modeling with  $\Delta\Delta\text{QTcF}$  as the dependent variable, time-matched concentration of OM as the explanatory variate, centered baseline QTcF (ie, baseline QTcF for individual subject subtracting the population mean baseline QTcF for all subjects in the same period) as an additional covariate, a fixed intercept, and subject as a random effect for both intercept and slope, when applicable.

The geometric mean of the individual  $C_{\text{max}}$  values for subjects on each of the active dose groups will be determined, respectively. The predicted population average  $\Delta\Delta\text{QTcF}$  (ie, slope estimate  $\times$  concentration + intercept) and its corresponding 2-sided 90% CI at the observed geometric mean  $C_{\text{max}}$  of OM will be obtained.

The plot of the observed median-quantile OM concentrations and associated mean  $\Delta\Delta\text{QTcF}$  (2-sided 90% CI) together with the regression line presenting the predicted  $\Delta\Delta\text{QTcF}$  (2-sided 90% CI; as described by Tornøe et al) will be used to evaluate the adequacy of the model fit to the assumption of linearity and the impact on quantifying the exposure response. For evaluation of the heart rate-corrected QT interval, a scatter plot and a quantile plot of QTcF and RR intervals by treatment with regression line and a linear mixed-effects line (90% CI), respectively, will also be given. Additional exploratory analyses (via graphical displays and/or model fitting) will include accounting for a delayed effect (hysteresis) and the justification for the choice of PD model (linear versus nonlinear) as follows.

#### 8.3.5.1. Investigation of Hysteresis

Hysteresis will be assessed based on joint graphical displays of the LS mean difference between  $\Delta\text{QTcF}$  under OM and under placebo ( $\Delta\Delta\text{QTcF}$ ) for each postdose timepoint and the mean concentrations of OM at the same timepoints. In addition, hysteresis plots will be given for LS mean  $\Delta\Delta\text{QTcF}$  and the mean concentrations. If a QT effect ( $\Delta\Delta\text{QTcF}$ )  $> 10$  msec cannot be excluded from the by-timepoint analysis and if a delay between peak  $\Delta\Delta\text{QTcF}$  and peak plasma concentration in the plot ( $\Delta\Delta\text{QTcF}$  versus OM) of more than 1 hour is observed, other C-QTc models, such as a model with an effect compartment, may be explored. With the

provision stated above, hysteresis will be assumed if the curve of hysteresis plot shows a counterclockwise loop.

### **8.3.5.2. Appropriate ness of a Linear Model**

To assess the appropriateness of a linear model, normal Q-Q plots for the standardized residuals and random effects, and plots of standardized residuals versus concentration and versus fitted values and versus centered baseline QTcF will be produced. The scatter plots of standardized residuals versus concentration and versus centered baseline QTcF by LOESS fitting (ie, locally weighted scatter plot smoothing as described by Cleveland) will also be produced with optimal smoothing parameters selected by the Akaike information criterion with a correction. A scatter plot of observed concentration and  $\Delta\Delta$ QTcF with LOESS line (90% CI) and linear regression line will also be provided to check the assumption of linear concentration-QTc relationship. If there is an indication that a linear model is inappropriate, additional models will be fitted, in particular, an  $E_{max}$  model.

The concentration-QTc analysis will then be repeated for the model found to best accommodate the nonlinearity detected.

## **8.4. Safety Analyses**

### **8.4.1. Adverse Events**

The number and percentage of subjects reporting any TEAEs will be tabulated by Medical Dictionary for Regulatory Activities system organ class and preferred term. Tables of fatal AEs, SAEs, AEs leading to withdrawal from IP or other protocol-required therapies, and significant TEAEs will also be provided. Subject-level data may be provided instead of tables if the subject incidence is low.

### **8.4.2. Clinical Laboratory Tests**

Key safety laboratory endpoints will be summarized in descriptive statistics. Details will be provided in the SAP.

### **8.4.3. Vital Signs**

The analyses of vital signs, including systolic BP, diastolic BP, pulse, and temperature, will be summarized using the descriptive statistics at each scheduled timepoint.

### **8.4.4. Physical Measurements**

The analyses of height, weight, and BMI measurements will include summary statistics at baseline.

### **8.4.5. Safety 12-Lead Electrocardiograms**

Summaries over time and/or changes from baseline over time will be provided for all safety ECG parameters. Subjects' maximum change from baseline in QTcF will be categorized and the number and percentage of subjects in each group will be summarized. Subjects'

Approved

maximum post-baseline values will also be categorized and the number and percentage of subjects in each group will be summarized.

## 8.5. Interim Analysis

No interim analyses are planned for this study.

## 10. APPENDICES

Approved

## Appendix 1: Safety Events: Definitions and Procedures for Recording, Evaluating, Follow-up and Reporting

### Definition of Adverse Event

Adverse Event Definition

• An adverse event (AE) is any untoward medical occurrence in a clinical study subject irrespective of a causal relationship with the study treatment.

• Note: An AE can therefore be any unfavorable and unintended sign (including an abnormal laboratory finding), symptom, or disease (new or exacerbated) temporally associated with the use of a treatment, combination product, medical device or procedure.

Events Meeting the Adverse Event Definition

• Any abnormal laboratory test results (hematology, clinical chemistry, or urinalysis) or other safety assessments (eg, electrocardiogram, radiological scans, vital signs measurements), including those that worsen from baseline, that are considered clinically significant in the medical and scientific judgment of the Investigator (ie, not related to progression of underlying disease).

• Exacerbation of a chronic or intermittent pre-existing condition, including either an increase in frequency and/or intensity of the condition.

• New conditions detected or diagnosed after study treatment administration even though it may have been present before the start of the study.

• Signs, symptoms, or the clinical sequelae of a suspected drug-drug interaction.

• Signs, symptoms, or the clinical sequelae of a suspected overdose of either study treatment or a concomitant medication. Overdose per se will not be reported as an AE/serious adverse event (SAE) unless it is an intentional overdose taken with possible suicidal/self-harming intent. Such overdoses are to be reported regardless of sequelae.

• The signs, symptoms, and/or clinical sequelae resulting from lack of efficacy will be reported as AE or SAE event if they fulfill the definition of an AE or SAE. Also, “lack of efficacy” or “failure of expected pharmacological action” also constitutes an AE or SAE.

Events NOT Meeting the Adverse Event Definition


• Medical or surgical procedure (eg, endoscopy, appendectomy): the condition that leads to the procedure is the AE.

• Situations in which an untoward medical occurrence did not occur (social and/or convenience admission to a hospital).

• Anticipated day-to-day fluctuations of pre-existing disease(s) or condition(s) present or detected at the start of the study that do not worsen.

Approved

## Definition of Serious Adverse Event

A Serious Adverse Event is defined as any untoward medical occurrence that, meets at least 1 of the following serious criteria:

Results in death (fatal)

Immediately life-threatening
 

The term “life-threatening” in the definition of “serious” refers to an event in which the subject was at risk of death at the time of the event. It does not refer to an event that hypothetically might have caused death, if it were more severe.

Requires in-patient hospitalization or prolongation of existing hospitalization
 

In general, hospitalization signifies that the subject has been detained (usually involving at least an overnight stay) at the hospital or emergency ward for observation and/or treatment that would not have been appropriate in the physician’s office or outpatient setting. Complications that occur during hospitalization are an AE. If a complication prolongs hospitalization or fulfills any other serious criteria, the event is serious. When in doubt as to whether “hospitalization” occurred or was necessary, the AE is to be considered serious. Hospitalization for elective treatment of a pre-existing condition that did not worsen from baseline is not considered an adverse event.

Results in persistent or significant disability/incapacity
 

The term disability means a substantial disruption of a person’s ability to conduct normal life functions. This definition is not intended to include experiences of relatively minor medical significance such as uncomplicated headache, nausea, vomiting, diarrhea, influenza, and accidental trauma (eg, sprained ankle) which may interfere with or prevent everyday life functions but do not constitute a substantial disruption.

Is a congenital anomaly/birth defect


Other medically important serious event
 

Medical or scientific judgment is to be exercised in deciding whether SAE reporting is appropriate in other situations such as important medical events that may not be immediately life-threatening or result in death or hospitalization but may jeopardize the subject or may require medical or surgical intervention to prevent 1 of the other outcomes listed in the above definition. These events are typically to be considered serious.

Examples of such events include invasive or malignant cancers, intensive treatment in an emergency room or at home for allergic bronchospasm, blood dyscrasias or convulsions that do not result in hospitalization, or development of drug dependency or drug abuse.

Approved

## Recording Adverse Events, and Serious Adverse Events

### Adverse Event and Serious Adverse Event Recording

- When an AE or SAE occurs, it is the responsibility of the Investigator to review all documentation (eg, hospital progress notes, laboratory, and diagnostics reports) related to the event.
- The Investigator will then record all relevant adverse event/serious adverse event information in the Event case report form (CRF).
  - Additionally, the Investigator is required to report a fatal event on the appropriate CRF.
- The Investigator must assign the following adverse event attributes:
  - Adverse event diagnosis or syndrome(s), if known (if not known, signs or symptoms);
  - Dates of onset and resolution (if resolved);
  - Severity (or toxicity defined below);
  - Assessment of relatedness to Amgen investigational product (IP): (OM/placebo), Non-Amgen protocol-required therapy (Moxifloxacin) and/or study-mandated procedures; and
  - Action taken.
- If the severity of an AE changes from the date of onset to the date of resolution, record as a single event with the worst severity on the appropriate CRF.
- It is not acceptable for the Investigator to send photocopies of the subject's medical records to Sponsor in lieu of completion of the appropriate CRF page.
- If specifically requested, the Investigator may need to provide additional follow-up information, such as discharge summaries, medical records, or extracts from the medical records. In this case, all subject identifiers, with the exception of the subject number, will be blinded on the copies of the medical records before submission to Amgen.
- The Investigator will attempt to establish a diagnosis of the event based on signs, symptoms, and/or other clinical information. In such cases, the diagnosis (not the individual signs/symptoms) will be documented as the AE/SAE.

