**Safety:**

The number and percentage of subjects reporting any TEAEs will be tabulated by Medical Dictionary for Regulatory Activities system organ class and preferred term and grouped by treatment. Adverse events, serious adverse events, clinical laboratory evaluations, ECGs, and vital signs measurements will be summarized by descriptive statistics.

Approved

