### **8.3.2. General Considerations**

Summary statistics for continuous variables will include number of subjects, mean, median, SD or standard error, minimum, and maximum. For categorical variables, frequency and percentage will be given.

Safety data will be analyzed and reported by treatment (OM, placebo, or moxifloxacin).

Statistical inferences will be provided for analyses of primary endpoints. Unless specified otherwise, all statistical tests are 2-sided with a significance level of 0.05; no statistical inference and imputation will be conducted for analyses of safety endpoints.

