- d Assessment to be performed at EOS only or if a subject is withdrawn early from the study.
- e ECGs will be extracted from the continuous 12-lead digital ECG recording as noted. The recording will be performed for approximately 27 hours in total. Subjects should lie down in a quiet room for at least 10 minutes before and 5 minutes after each extraction at the timepoints listed.
- f Adverse events (AEs) are collected from the time of the first dose of study treatment to EOS. Events occurring prior to the first dose in Part B but after dosing in Part A will be reported as occurring in Part A.
- g Serious adverse events (SAEs) are collected from the time the ICF is signed until 30 days after the last dose.
- h Urine pregnancy tests will be used on Day -1 of each dosing period and at EOS.
- i Predose vital signs measurements and safety ECGs are to be performed prior to the start of continuous cardiac monitoring.
- j Treatments will be separated by a washout period of  $\geq 7$  days.
- k Treatment will be administered after all predose procedures are completed and after at least a 10-hour fast.
- l Pharmacokinetic (PK) samples should be collected within 5 minutes after the completion of the digital ECG extraction window through 24 hours postdose and within  $\pm 2$  hours of the digital ECG extraction windows after 24 hours postdose. Samples collected outside of this window should still be collected and recorded as protocol deviations.
- n Collect only on Day -1 of Period 1.

Approved

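### Appendix 1 merges a worsening AE into one record with no date of change, so in this crossover a worsening after a later dose may be attributed to the wrong treatment

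*Protocol*

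**What the plan says.** Protocol Appendix 1, on recording AEs and SAEs, instructs the investigator: where "severity of an AE changes from the date of onset to the date of resolution, record as a single event with the worst severity". The dates required for each event are "Dates of onset and resolution (if resolved"). Severity, relatedness and action taken are also required. A date of severity change is not.

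The safety data are then split by treatment. Protocol Section 8.3.2 states: "Safety data will be analyzed and reported by treatment (OM, placebo, or moxifloxacin"). The synopsis has TEAEs "tabulated by Medical Dictionary for Regulatory Activities system organ class and preferred term and grouped by treatment". Subject incidence of TEAEs is a secondary endpoint (Section 2.2.2).

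Two other places bear on the point. Appendix 1 counts as an AE: "Exacerbation of a chronic or intermittent pre-existing condition, including either an increase in frequency and/or intensity of the condition". Footnote f to the Part B schedule in Appendix 6 gives the only timing rule: "Events occurring prior to the first dose in Part B but after dosing in Part A will be reported as occurring in Part A".

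The protocol uses the term TEAE but does not define it. The supplied SAP is confined to ECG and concentration-QTc analyses (SAP Section 2) and has no AE rules.

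**The concern.** One record with one worst grade is adequate when a subject receives one treatment. Here each Part B subject takes 25-mg OM in Part A and then placebo, 50-mg OM and moxifloxacin in one of six orders. An AE can begin under one treatment, still be present at the next dose, and become worse after it. A record with a single onset date and a single grade cannot show that. The placebo period is the control for OM tolerability, so an event or grade held under the wrong period distorts the comparison that the by-treatment tables are meant to give.

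A rule that counts AEs that start or worsen after a dose would solve this at the analysis stage, but only if the data show when the worsening occurred. The loss is therefore at data capture, and a later analysis plan cannot fully repair it.

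**Working it through.** The plan gives no figure to reproduce. The check sets the rules side by side, lists the sequences, and sizes one affected subject.

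**Inputs.** Six sequences with 10 subjects each, 60 in Part B, about 48 evaluable in all three periods (Protocol Sections 3.1 and 8.1); A = placebo, B = 50-mg OM, C = moxifloxacin; washouts of at least 7 days, including between Parts A and B (Section 3.1).

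**Step 1: does another rule repair the record?**
- Footnote f separates Part A from Part B by time of occurrence. It is silent on Periods 1 to 3 and on worsening.
- The exacerbation clause concerns chronic or intermittent pre-existing conditions and is not tied to a new period. For an AE already under way, the single-record instruction is the more specific one.
- The causality field does not identify the treatment, because OM and placebo share one investigational-product category in Appendix 1.
- Section 8.3.2 rules out imputation for safety endpoints, so a missing date of worsening would stay missing.

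**Step 2: what surrounds 50-mg OM?**

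| Sequence | Order | Immediately before B | Immediately after B |
|---|---|---|---|
| 1 | A B C | placebo | moxifloxacin |
| 2 | B C A | 25-mg OM (Part A) | moxifloxacin |
| 3 | C A B | placebo | none |
| 4 | A C B | moxifloxacin | none |
| 5 | C B A | moxifloxacin | placebo |
| 6 | B A C | 25-mg OM (Part A) | placebo |

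The treatment immediately before 50-mg OM is placebo in 2 of 6 sequences, moxifloxacin in 2 and 25-mg OM in 2, or 2 × 10 = 20 planned subjects each. A non-OM treatment comes immediately before 50-mg OM in 4 of 6 sequences and immediately after it in 4 of 6. Over any distance, 50-mg OM precedes placebo in sequences 2, 5 and 6, and moxifloxacin in 1, 2 and 6.

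**Step 3: two mirror cases, assuming assignment by onset and no other event in the same table row.**
- *Starts on placebo, worsens after 50-mg OM.* The tables show placebo 1, OM 0. A starts-or-worsens count would show placebo 1, OM 1. OM minus placebo is too low by 1/60.
- *Starts on 50-mg OM, worsens after placebo.* The tables show OM 1, placebo 0, and the worst grade sits under OM. A starts-or-worsens count would show OM 1, placebo 1. OM minus placebo is too high by 1/60.

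With *a* subjects of the first kind and *b* of the second, the error in OM minus placebo is (*b* − *a*)/60. It is negative, zero or positive according to *a* and *b*, which the documents do not give.

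**Step 4: size.** Each subject whose only OM event in a row is an uncounted worsening lowers OM incidence in that row by 1/60 = 1.7 points, or 1/48 = 2.1 points if only 48 contribute. For an assumed 1 to 3 such subjects the range is 1.7 to 3/60 = 5.0 points, or 2.1 to 3/48 = 6.3 points. In sequences 2 and 6 an AE carried over from Part A began on 25-mg OM. If both OM doses are tabulated together, as the three categories in Section 8.3.2 suggest, the pooled OM incidence does not change.

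**The case against.** A reader might infer that the plan systematically understates OM harm, with the worsened event certain to be tabulated under the earlier treatment. The documents do not support that. Appendix 1 governs recording, not tabulation, and assignment by first onset is not written for Part B. As Step 3 shows, the same rule can also leave a worsening that followed placebo or moxifloxacin under OM, so no direction can be claimed.

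A reader might also infer a doubled effect for severe events, lost from OM and added to placebo. Section 8.4.1 lists no table by severity, so that contrast is not a planned output.

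Other objections have weight:
- The protocol refers to an SAP for safety detail as well as to a Cardiac SAP. A safety SAP or the eCRF completion instructions, neither supplied, may settle assignment.
- Subjects are resident throughout Part B and questioned at least daily, so source notes might show when an AE worsened.
- An AE starting around one dose must last about 7 days or more to be open at the next, although one starting late in the washout need not.
- A subject with another new OM event in the same row is still counted.
- Safety analysis is descriptive and the primary QTcF endpoint is unaffected.

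These limit the size and the certainty. They do not remove the gap: the CRF is not required to hold the date that a rule counting worsening after a dose would need, and recovery from source is possible but not planned.

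**Conclusion.** The concern holds as a defect in AE capture for a crossover. The single-record rule has no exception for a new treatment period, so the record cannot show a worsening after a later dose, and by-treatment incidence may be misattributed. The shift is about 1.7 points in OM incidence per affected subject, on 60 subjects. It rests on assignment by onset, on the AE being open at the later dose, and on the subject having no other OM event in that row. The number of such subjects is not given and should be small. The net direction is unknown. The point is modest in size, but it concerns a secondary endpoint and is cheap to correct.

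**What to change.** In Appendix 1, limit the single-record, worst-severity sentence to severity changes within one treatment period. Add that if an AE ongoing at a later period's dose (including from Part A into Part B) worsens after that dose, a new linked record is opened with its own onset date and time, severity, relatedness and action taken. Capturing the date of each severity change on the existing record would be an alternative.

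In Section 8.4.1, count an AE under a treatment if it starts or worsens after that period's dose and before the next dose. Any separate safety SAP should use the same definition.

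The cost is one sentence in each place and a matching eCRF completion instruction. The number of AE records rises slightly, because one illness can give two linked records; the count of subjects with an AE within a treatment is not inflated. Where records already exist, their onset and resolution dates identify AEs that were open at a later dose, and source notes can be checked for those alone.

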### Evaluating Adverse Events and Serious Adverse Events

#### Assessment of Severity

The Investigator will make an assessment of severity for each AE and SAE reported during the study. The assessment of severity will be based on:

#### The Amgen Standard Grading Scale as show below:

Grade	Definition
Grade	Definition

Approved

MILD	Aware of sign or symptom, but easily tolerated
MODERATE	Discomfort enough to cause interference with usual activity
SEVERE a	Incapacitating, with inability to work or do usual activity

a An event is defined as 'serious' when it meets at least 1 of the predefined outcomes as described in the definition of an SAE, NOT when it is rated as severe.
	
Assessment of Causality	

• The Investigator is obligated to assess the relationship between IP (OM/placebo), protocol-required therapy (Moxifloxacin) and/or study-mandated procedure and each occurrence of AE/SAE.

• Relatedness means that there are facts or reasons to support a relationship between IP and the event.

• The Investigator will use clinical judgment to determine the relationship.

• Alternative causes, such as underlying disease(s), concomitant therapy, and other risk factors, as well as the temporal relationship of the event to study treatment administration will be considered and investigated.

• The Investigator will also consult the Investigator's Brochure and/or Product Information, for marketed products, in his/her assessment.

• For each AE/SAE, the Investigator must document in the medical notes that he/she has reviewed the AE/SAE and has provided an assessment of causality.

• There may be situations in which an SAE has occurred and the Investigator has minimal information to include in the initial report. However, it is very important that the Investigator always make an assessment of causality for every event before the initial transmission of the SAE data.

• The Investigator may change his/her opinion of causality in light of follow-up information and send an SAE follow-up report with the updated causality assessment.

• The causality assessment is 1 of the criteria used when determining regulatory reporting requirements.

	
Follow-up of Adverse Event and Serious Adverse Event	


• The Investigator is obligated to perform or arrange for the conduct of supplemental measurements and/or evaluations as medically indicated or as requested by Amgen to elucidate the nature and/or causality of the AE or SAE as fully as possible. This may include additional laboratory tests or investigations, histopathological examinations, or consultation with other health care professionals.

• If a subject is permanently withdrawn from IP/protocol-required therapies because of an SAE, this information must be submitted to Amgen.

	

Approved

- If a subject dies during participation in the study or during a recognized follow-up period, the Investigator will provide Amgen with a copy of any post-mortem findings including histopathology.
- New or updated information will be recorded in the originally completed eCRF.
- The Investigator will submit any updated SAE data to Amgen within 24 hours of receipt of the information.

